1 PROTOCOL SUMMARY

1.1 SYNOPSIS

Title: Residential MapTrek

Grant Number: UL1TR002537

Study Description:

The overarching goal of our project is to develop an inexpensive and scalable tool to increase volume of physical activity in our target population, older adults living in a residential facility. MapTrek is a web-based application that allows participants to take a virtual walk in interesting locations around the world while tracking their progress against the progress of other older adults living in a retirement community. Steps are counted using a commercially available accelerometer (e.g., Fitbit), and participants see their progress overlaid on Google Maps. The overarching goal of our project is to develop an inexpensive and scalable tool to increase volume of physical activity in our target population, older adults living in a residential facility.

All participants will be provided with a Fitbit activity monitor and instructed to wear it 24 hours/day (except for bathing/swimming time) on their wrist for 12 weeks. Participants will participate in four team based walking races, each two weeks long. Participants will view their team progress on TV monitors placed in various locations at the Oaknoll facility. The monitors will present aggregated team data and will not report any individual data that could link back to the individual participant.

At the end of the 8 week active intervention, research team members will meet with participants at Oaknoll to administer an exit/process evaluation survey. The exit survey will ask about psychosocial predictors of physical activity as well as participants thoughts and opinions of the MapTrek game. This survey should take approximate 10-15 minutes to complete. We will then ask the participants to wear the Fitbit for four more weeks without playing MapTrek, which will act as a control condition since this is a single-arm study.

Objectives*:

Primary Objective: 1. To determine the efficacy of MapTrek

for improving physical activity levels of older adults living in a residential facility.

Secondary 1. To determine the efficacy of MapTrek for Objectives: improving psychosocial outcomes(e.g., self-

efficacy, social support, outcome

Residential MapTrek Version 1.007
Protocol 201904816 28 August 2019

expectations) among older adults living in a

residential facility.

2. To determine the acceptability of MapTrek among older adults living in a residential

facility.

Endpoints*: Primary Endpoint: 8-week active intervention (August 26,

2019)

Secondary 4-week follow up (September 22, 2019)

Endpoints:

Study Population: Adults (25-64 years) and older adults (65+ years)

Phase* or Stage:

Description of Sites/Facilities One retirement community **Enrolling Participants:**

Description of Study Intervention/Experimental Manipulation: All participants will then be provided with a Fitbit activity monitor and instructed to wear it 24 hours/day (except for bathing/swimming time) for the next 4 days. After 4 days of baseline data collection, our team will assign participants to one of three teams through randomization based on their baseline activity data. The three teams will be identified by three colors of wrist bands that hold the Fitbit monitor; black white and teal.

After baseline data collection, the research team will hold a kick-off event for the participants. The research team will give a brief presentation describing the study again. Participants will be informed of their team by a research team member and will be provided a wrist band that corresponds to their team color (black, white or teal). At that point, participants will receive written instructions ("game rules") on how to play the MapTrek intervention (our virtual walking race platform).

[figure not shown]
As part of the MapTrek game, participants will be asked to wear their Fitbit activity monitor every day for 12 weeks. For the first eight weeks, participants will participate in four team based walking races, each two weeks long. Participants will view their team progress on TV monitors placed in various locations at the Oaknoll facility. The Oaknoll leadership has given us approval to do this at their facility (see letter of support). The monitors will present aggregated team data and will not report any individual data that could link back to the individual participant. After the 8-week active intervention, we will take MapTrek away and will ask participants to wear the Fitbit for an additional 4 weeks. This will be done to determine the effects of MapTrek had on physical activity compared to a control where participants only wear the Fitbit.

Study Duration*: 12 weeks

Participant Duration: 13 weeks

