6 STUDY INTERVENTION(S) OR EXPERIMENTAL MANIPULATION(S)

6.1 STUDY INTERVENTION(S) OR EXPERIMENTAL MANIPULATION(S) ADMINISTRATION

6.1.1 STUDY INTERVENTION OR EXPERIMENTAL MANIPULATION DESCRIPTION

We enrolled two different intervention groups, a group of older adults who live at Oaknoll and a group of Oaknoll employees. Enrolling a group of Oaknoll employees served two functions. First, it exposed the employees to MapTrek so that they can assist the residents with any technical problems or questions they may have during the course of the project period. Second, it fostered intergenerational engagement and generate excitement throughout the entire facility. Third, including employees was another avenue to increase social support for older adults, addressing the interpersonal level of the SEM. Physical activity interventions are likely to have greater effects when different levels are addressed at the same time.

At enrollment, each participant was provided with a Fitbit, shown how to wear it, and consented to the research team accessing their Fitbit data. Participants were asked to complete a baseline survey which asked about demographic information, their self-efficacy for exercise, social support for exercise, outcome expectations for exercise, and social isolation. Total participation in this project lasted for 14 weeks. The first two weeks were used to collected baseline data, where participants wore their Fitbit, but did not receive access to the MapTrek intervention. During the baseline period a kick-off event was held to answer participant's questions, and to give participants their team colored wrist bands. Participants were placed into one of three teams, and stayed on these teams for the duration of the intervention. Three teams were used to help foster competition in the event that one team was walking significantly more or less steps than the others.

After the two-week baseline period, participants received access to MapTrek and competed in four, two week-long races. Four two-week races were used so that teams had the opportunity to walk meaningful distances along each route (e.g., walking on the Grand Canyon Trail). The teams were assigned a new virtual walking route every two weeks. The team with the most steps at the end of two weeks were the winners.

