9 STATISTICAL CONSIDERATIONS

9.1 STATISTICAL HYPOTHESES

- Primary Efficacy Endpoint(s): We hypothesize that participants will increase their average steps/day from
 baseline to the initial adoption of the active intervention, there will be a significant difference in average
 steps/day from baseline to the last week of the active intervention, there will be a significant difference in
 average steps/day from baseline to the follow-up phase post-active intervention, participants will
 experience a decrease in average steps/day each day from the start of the 8-week intervention to the
 end. two to week eight.
- Secondary Efficacy Endpoint(s): We hypothesize participants will increase their feelings of social support, self-efficacy, and outcome expectations, and decrease their feeling of social isolation from baseline to post-active intervention. We hypothesize this will be an acceptable multilevel mHealth intervention among older adults living in a retirement community.

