9.4.2 ANALYSIS OF THE PRIMARY ENDPOINT(S)

We will used mixed-effect models to Repeated measures ANOVA.

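### If the 4-day window is the baseline, the step contrasts can carry a weekday/weekend error that the primary analysis does not adjust for; the two stated baseline lengths must be reconciled

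*Combined protocol and SAP*

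**What the plan says.** The documents give two baseline lengths.

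- **Synopsis (1.1):** "After 4 days of baseline data collection, our team will assign participants" to teams, using their activity in those days. It also gives "Participant Duration: 13 weeks".
- **Section 6.1.1:** "The first two weeks were used to collected baseline data, where participants wore their Fitbit, but did not receive access to the MapTrek intervention", and again "After the two-week baseline period, participants received access to MapTrek and competed in four, two week-long races". It adds: "Total participation in this project lasted for 14 weeks".
- **Section 8.1:** thirteen weeks of wear in one sentence and 12 weeks in another.

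The kick-off event comes after baseline in the Synopsis and during it in 6.1.1.

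The primary hypotheses in 9.1 compare baseline with initial adoption, with the end of the active phase ("steps/day from baseline to the last week of the active intervention") and with the follow-up phase. They do not say which calendar days form the baseline mean or how long initial adoption lasts.

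The whole of 9.4.2 is one sentence: "We will used mixed-effect models to Repeated measures ANOVA". It names no model terms. Section 8.1 says Fitbit data are available by the minute for each day worn, so the day of the week is known for every step count.

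**The concern.** The study is single-arm and pre-post, so no concurrent group cancels a calendar effect. If residents or staff walk different amounts on weekdays and weekends, a reference period with the wrong weekend share shifts the estimated change even when behaviour has not altered.

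The last active week and the 4-week follow-up consist of whole weeks. Four consecutive days cannot match that mix. If many participants share the same four days, the shift falls in the same direction for all of them. It then does not shrink as more people are enrolled, and the standard error does not show it. Part of an apparent MapTrek gain, or part of a missed one, could be a calendar effect.

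**Working it through.** **Inputs from the documents.** Baseline of 4 days (1.1) or two weeks (6.1.1). Comparison with a whole last week and a 4-week follow-up (9.1, 1.1). Target difference 1,750 steps, SD 2,000, significance level 0.05, power 80%, n = 42 (9.2).

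**Input not in the documents.** D, the mean weekday minus the mean weekend steps/day. I assume 250, 500 and 1,000, with weekends lower. If weekends are higher, every sign below reverses.

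**The plan's own figure.** Two independent groups, two-sided: 2 × [2,000 × (1.960 + 0.842) / 1,750]² = 20.5, so 21 per group and 42 in total. The stated 42 is reproduced on that basis. Here only the 1,750-step target is used, as a yardstick.

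**Step 1: what the stated durations imply.** The active phase and follow-up take 8 + 4 = 12 weeks. A total of 14 weeks leaves 2 weeks for baseline and a total of 13 leaves 1 week. Neither equals 4 days.

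**Step 2: error formula.** Let W be the weekday mean and f the weekend share of the baseline, with no true change.

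- Baseline mean = W - fD
- Whole-week mean = W - (2/7)D
- Error in the change = (f - 2/7)D

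**Step 3: every 4-day window, error in steps/day.**

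| Start day | f | f - 2/7 | D = 250 | D = 500 | D = 1,000 |
|---|---|---|---|---|---|
| Mon, Tue | 0 | -0.286 | -71 | -143 | -286 |
| Wed, Sun | 0.25 | -0.036 | -9 | -18 | -36 |
| Thu, Fri, Sat | 0.50 | +0.214 | +54 | +107 | +214 |

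As a share of 1,750 steps, the extremes are -4.1% to +3.1% (D = 250), -8.2% to +6.1% (D = 500) and -16.3% to +12.2% (D = 1,000).

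**Step 4: start days spread evenly over the week.** [2 × (-0.286) + 2 × (-0.036) + 3 × 0.214] / 7 = 0 to rounding. The mean error vanishes, and what remains is extra variation between people.

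**Step 5: two-week baseline.** Any 14 consecutive days contain 4 weekend days, so f = 4/14 = 2/7 and the error is 0 for every D. If one weekend day is not worn, f = 3/13 = 0.231 and the error is (0.231 - 0.286)D = -0.055D, or -55 steps/day at D = 1,000. This biases the group mean only if missing days fall unevenly on weekdays and weekends, and differently in baseline and the later phase.

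**The case against.** The strongest objection is that the 4-day premise is contested. Section 6.1.1 gives two weeks twice, in the past tense, and a fully worn 14-day baseline has no calendar error. The Synopsis ties the 4 days to forming teams, and 9.1 does not say that those days are the reference for the step contrasts. This stands, and it makes the point conditional.

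Second, a reader might infer that the error is systematic. The documents do not support that. It needs a real weekday/weekend difference, which they do not report, and shared or uneven start days. Fitbits are issued at enrolment (6.1.1) and accrual runs over 2 weeks (5.5), which suggests staggered windows. A reader might also count back 56 days from 26 August 2019 to Monday 1 July and conclude that baseline ran Thursday to Sunday. But no baseline dates are given, and the Synopsis places team assignment and a kick-off between baseline and the races.

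Third, two of the seven start days include one weekend day, and the error is then negligible: 36 steps/day at D = 1,000.

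Fourth, 9.4.2 names no terms at all, so the missing day-of-week term is part of a wider gap. That is true, but this term has a specific job when the reference period is not made of whole weeks. Settling on two weeks would not cover unevenly missing days, or an initial-adoption window shorter than a week.

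**Conclusion.** The point holds conditionally. The baseline length and the days that form the baseline mean are not settled, and the passages must be reconciled. If a 4-day window is the reference, each contrast with a whole-week period can be shifted by -0.286D, -0.036D or +0.214D steps/day. At an assumed D of 1,000 the extremes are -286 and +214, at most about a sixth of the 1,750-step target. At D = 250 they are -71 and +54.

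This rests on an assumed D, complete wear, and start days that are shared or unevenly spread. With evenly spread start days, or a fully worn two-week baseline, the mean error is zero.

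A reader might go further and infer that the primary result is biased in favour of MapTrek. The documents do not support that: with lower weekends, a baseline without weekend days understates the gain, and neither the start days nor the sign of D is known. The initial-adoption contrast cannot be sized at all, because its window is undefined.

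**What to change.** 1. Reconcile 1.1, 6.1.1 and 8.1 on baseline length and total duration. State in 9.1 which calendar days form the baseline mean and the initial-adoption mean.
2. In 9.4.2, fit the mixed model to daily step counts with phase and day of week (or at least a weekend indicator) as fixed effects. Report phase means, and the contrasts of baseline with initial adoption, last week and follow-up, standardised to a week of 5/7 weekdays and 2/7 weekend days.
3. State the limitation. Where a baseline has no weekend day, its weekend level is borrowed from later phases, so the adjustment assumes that the weekday/weekend difference is the same in every phase. A weekday-only comparison would be a simple check in that case.

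The cost is a few sentences and one to six extra model terms, estimated from data already collected. It is a cheap improvement but not a free one, because of the assumption in item 3.

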3 OBJECTIVES AND ENDPOINTS

OBJECTIVES	ENDPOINTS	JUSTIFICATION FOR ENDPOINTS	PUTATIVE MECHANISMS OF ACTION
Primary			
1. To determine the efficacy of MapTrek for improving physical activity levels of older adults living in a residential facility.	Assessments made at baseline, 8 weeks and 12 weeks.	We will determine whether the intervention was effective at 8 weeks and whether participants maintained outcomes at 12 weeks.	
Secondary			
1. To determine the efficacy of MapTrek for improving psychosocial outcomes(e.g., self-efficacy, social support, outcome expectations) among older adults living in a residential facility.		We will determine whether the intervention was effective at 8 weeks and whether participants maintained outcomes at 12 weeks.	
2. To determine the acceptability of MapTrek among older adults living in a residential facility.	We will assess acceptability at 8 weeks.	Participants will have just finished the intervention at 8 weeks.	
Tertiary/Exploratory			

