9.2 SAMPLE SIZE DETERMINATION

To achieve 80% power to detect a 1,750 step difference in step counts between the pre- and post-intervention periods, with a standard deviation of 2,000 steps and a significance level of 0.05, we are required to enroll at least 42 participants. If we add an additional 25% for possible drop outs, we will need to enroll at least 50 participants into the older adult group.

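### Weeks 9–12 are a control in section 1.1 and a maintenance check in section 3, and section 9 names no active-versus-follow-up contrast or reading that would settle which

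*Combined protocol and SAP*

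**What the plan says.** Section 1.1 assigns the control role twice. The study description says of the four further weeks of Fitbit wear without the game: "which will act as a control condition since this is a single-arm study". The description of the intervention gives the purpose: "This will be done to determine the effects of MapTrek had on physical activity compared to a control where participants only wear the Fitbit".

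Section 3, in the row for the primary objective, gives the later time point a different role: "We will determine whether the intervention was effective at 8 weeks and whether participants maintained outcomes at 12 weeks".

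Section 9.1 lists four primary hypotheses on steps: baseline to initial adoption, baseline to the last active week, a difference in "average steps/day from baseline to the follow-up phase post-active intervention", and a daily decline within the active phase. The follow-up hypothesis has no direction. Section 9.2 sizes a 1,750-step difference between the pre- and post-intervention periods. Section 9.4.2 is a single unfinished sentence naming mixed-effect models and repeated-measures ANOVA.

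On rank, the synopsis lists "Primary Endpoint: 8-week active intervention (August 26", 2019), and gives as secondary "4-week follow up (September 22, 2019"). Section 3's primary row lists assessments at baseline, 8 weeks and 12 weeks, and 9.1 puts follow-up under the primary endpoint.

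**The concern.** In a single-arm study, weeks 9–12 are the only Fitbit-only comparison apart from baseline, and section 1.1 relies on them for that. A control and a maintenance check give opposite verdicts on the same result. If steps hold after MapTrek is removed, the maintenance reading says success and the control reading says MapTrek added nothing to the Fitbit. If steps fall, the verdicts swap. Section 9 fixes neither the contrast, nor the active window it would use (whole phase or last week), nor the reading. Followed as written, the plan does not deliver the control comparison it announces, and the interpretation can be chosen after the result is known.

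A second problem is order. Weeks 9–12 follow the active phase for everyone, so active minus weeks 9–12 mixes removal of MapTrek with carry-over and with any continuing decline in Fitbit-only steps. Section 4.2 reports such a decline in the earlier office-worker trial: both groups drifted back towards baseline, the control group at 24.3 steps/day.

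**Working it through.** **The plan's own figure.** The 42 in 9.2 reproduces from the formula for two independent groups: 2 × [(1.96 + 0.84) × 2,000 / 1,750]² = 20.5, so 21 per group and 42 in total. It is tied to pre versus post. No sample-size statement concerns active versus weeks 9–12, and the point here does not depend on the 42.

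**What section 9 implies.** Write B for baseline, L for the last active week and F for weeks 9–12. Section 9.1 names L − B and F − B. The missing contrast is their difference, (L − B) − (F − B) = L − F. It can be estimated, but it is not named or interpreted.

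**One result, two claims.** Suppose the planned 1,750-step gain is reached and half is retained. Then F − B = 875 (retained gain) and L − F = 1,750 − 875 = 875 (loss on removal). The same data support a claim of maintenance and a claim of a MapTrek effect. Section 9.2 plans "with a standard deviation of 2,000 steps and a significance level of 0.05" but does not say whether that SD is per period or of the change. Taken per period, the SD of change is 2,000 × √(2(1 − r)). With n = 42, two-sided 0.05 and assumed r = 0.3, 0.5, 0.7 or 0.8, a paired t-test has power 0.65, 0.79, 0.95 or 0.99 for 875 steps. Each claim could readily reach significance on its own.

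**Time trend with zero MapTrek effect.** Inputs:
- the decline of 24.3 steps/day (section 4.2);
- days 1–56 active, 50–56 the last active week, 57–84 follow-up, each day taken at its midpoint;
- an assumed Fitbit-only rise A of 500, 1,000 or 1,500 steps (not in the documents);
- fading that starts with MapTrek, 4 days earlier (the baseline in 1.1) or 14 days earlier (the baseline in 6.1.1).

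Two shapes were used: exponential, A·exp(−24.3t/A), and linear to a floor, max(A − 24.3t, 0).

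Example (floor, A = 1,500, fade from MapTrek start): the active mean is 1,500 − 24.3 × 28 = 819.6. The last-week mean is 1,500 − 24.3 × 52.5 = 224.2. The floor is reached at day 1,500/24.3 = 61.7, so the weeks 9–12 mean is 14.2. The differences are 805 and 210.

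| Fade starts | Shape | Whole phase − weeks 9–12 (A = 500 / 1,000 / 1,500) | Last active week − weeks 9–12 |
|---|---|---|---|
| MapTrek start | exponential | 154 / 360 / 499 | 21 / 94 / 154 |
| MapTrek start | floor | 92 / 367 / 805 | 0 / 0 / 210 |
| 4 days earlier | exponential | 127 / 327 / 468 | 17 / 85 / 145 |
| 4 days earlier | floor | 60 / 299 / 721 | 0 / 0 / 126 |
| 14 days earlier | exponential | 78 / 256 / 398 | 11 / 67 / 123 |
| 14 days earlier | floor | 9 / 160 / 494 | 0 / 0 / 0 |

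For a 250-step rise with the 14-day lead, the floor is reached at 250/24.3 = 10.3 days, before MapTrek starts, and the bias is 0.

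**Carry-over works the other way.** With a true effect of 1,000 steps decaying after removal with a half-life of 3, 7 or 14 days, last active week minus weeks 9–12 gives 846, 662 or 459. A level change at the boundary, from a line fitted in each phase, gives 526, 244 or 96. In the 18 zero-effect scenarios above, that level change is negative in 16.

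**The case against.** The strongest reply is that section 1.1 does state the comparison, that a mixed model over the three periods can estimate it, and that a withdrawal phase can legitimately inform both effect and persistence. All of this stands. It would be wrong to say that the comparison appears nowhere or cannot be computed. What remains is that the hypotheses and analysis sections do not turn the stated purpose into a contrast with a window and a reading. The window matters under 9.1 itself, which expects steps to decline during the active phase.

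It can also be said that this is a pilot whose synopsis places primary efficacy at 8 weeks. That limits the damage, so the pre-post result at 8 weeks is less exposed. But the documents do not agree on rank. A reader might infer that 9.1 alone is out of line in treating follow-up as primary. It is not, because section 3's primary row also includes 12 weeks.

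A reader might infer from the version line, "Protocol 201904816 28 August 2019", that the follow-up reading could have been fitted to the data. The dates do not support this. 28 August is two days after the stated 8-week date, and follow-up runs to 22 September, so almost no follow-up data could have existed. Active-phase data would have existed, but nothing shows that they had been examined, and a version date does not show when section 9 was written.

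**Conclusion.** The point holds and should be fixed. Section 1.1 and section 3 give weeks 9–12 different roles, and section 9 names no contrast, window or reading that chooses between them. The consequence is an interpretation left open in both directions, not an invalid 8-week analysis.

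The trend bias is conditional. A reader might infer that active minus weeks 9–12 must be above zero even if MapTrek does nothing. The documents give no Fitbit-only rise for this population, and with a small rise the bias is near zero. If there is a rise of 500–1,500 steps that fades at the office-worker rate, the bias is about 10–800 steps for the whole-phase mean and 0–210 for the last active week. An unbroken linear decline would give 24.3 × 42 = 1,021, but it needs a fall of 24.3 × 84 = 2,041 steps over 12 weeks, whereas section 4.2 describes a return towards baseline. That figure should not be used as the expected size. The confidence is high for the conflict between sections and lower for any particular number of steps.

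**What to change.** 1. In both places in section 1.1, replace the control wording with *withdrawal (Fitbit-only) phase*.
2. Reconcile the synopsis endpoints, section 3 and 9.1 on rank: last active week versus baseline, the window 9.1 already uses, as the primary pre-post contrast, and follow-up as secondary.
3. In 9.1 and 9.4.2, name last active week minus weeks 9–12 as the single secondary withdrawal contrast, estimated from the mixed model already planned. Report weeks 9–12 versus baseline beside it as *retained gain*, with its direction stated, so that partial loss is visible.
4. State that the withdrawal contrast estimates MapTrek versus Fitbit-only only if there is no carry-over and no underlying time trend, that no drop does not show no effect, and that sustained steps do not show a MapTrek-specific effect. A trend-adjusted level change may be reported as a sensitivity analysis, but should not gate the conclusion. It recovers only 244 of a true 1,000 steps under a 7-day half-life, so requiring both intervals to exclude zero would often hide a real effect.
5. Date the change and state which outcome data had been seen. If follow-up data had been seen, the contrast cannot be called prospective.

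The cost is wording in sections 1.1, 3, 9.1 and 9.4.2 and slightly more analysis of Fitbit data already being collected, with no new visits or data. The conclusion about MapTrek itself becomes more cautious.

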4 STUDY DESIGN

4.1 OVERALL DESIGN

This intervention is a single arm, pre-post test pilot study.

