Our team has developed a mHealth intervention called MapTrek (Gremaud et al., 2018). MapTrek is a mobile-phone based walking game, grounded in behavioral theory that places participants into virtual walking races for the purpose of encouraging more daily physical activity throughout the day. MapTrek was designed to be fun, engaging and interactive. In a recent trial, we found MapTrek to be feasible and efficacious at increasing physical activity among healthy sedentary office workers (Gremaud et al., 2018). Participants were randomized to a MapTrek intervention or a Fitbit control group. Participants in the MapTrek group took an average of 1,455 more steps/day than the control group. At the start of the intervention, MapTrek participants immediately increased their steps by 2,183 steps/day beyond the control group. After the intervention started, both groups started to decrease their average steps/day back to baseline values. The MapTrek group decayed significantly faster at 44.8 steps/day compared to the control group at 24.3 steps/day. Conversely, 70.9% of participants reported MapTrek increased their perceived level of support to be physically active, 77.7% felt motivated to be more active, 70.2% reported MapTrek was a fun, and 93.1% of participants reported MapTrek was easy to play (Gremaud et al., 2018). While these outcomes suggest MapTrek was effective for middle-aged adults in the community, we have not yet tested this approach among older adults. We believe MapTrek could be adapted for use and effective for increasing physical activity levels of older adults living in retirement communities. With the large and growing number of inactive older adults in the U.S., it is crucial that we identify effective and scalable approaches for promoting physical activity among older adults.

Translation of interventions to a population level has been slow and inconsistent. Significant effects on health can be made through widespread adoption and dissemination of interventions (Gonzales, Handley, Ackerman, & O'Sullivan P, 2012)

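### The Fitbit-only control weeks follow MapTrek for every participant, and the plan gives no contrast or time term to separate MapTrek's removal from ordinary decline in steps

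*Combined protocol and SAP*

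**What the plan says.** Section 4.1 describes the design: "This intervention is a single arm, pre-post test pilot study". Section 1.1 sets the order of the phases. First come the races: "For the first eight weeks, participants will participate in four team based walking races, each two weeks long". MapTrek is then withdrawn: "We will then ask the participants to wear the Fitbit for four more weeks without playing MapTrek, which will act as a control condition". The synopsis also gives the purpose of those four weeks: "This will be done to determine the effects of MapTrek had on physical activity compared to a control where participants only wear the Fitbit".

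Section 4.2 summarises the team's randomised trial in sedentary office workers, which had a concurrent Fitbit-only group. Both groups drifted back towards their baseline after the start: "The MapTrek group decayed significantly faster at 44.8 steps/day compared to the control group at 24.3 steps/day".

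Section 9.1 lists three step contrasts, all against baseline (initial adoption, last active week, follow-up phase). It adds a prediction that participants will "experience a decrease in average steps/day each day from the start of the 8-week intervention". It does not compare the active phase with follow-up. The whole primary analysis in Section 9.4.2 reads: "We will used mixed-effect models to Repeated measures ANOVA".

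**The concern.** The primary objective is the efficacy of MapTrek, and weeks 9-12 are the plan's means of telling MapTrek apart from simply wearing a Fitbit. Treatment and calendar time are fully aligned in that comparison, because everyone has MapTrek first and Fitbit-only second. If steps decline with time anyway, weeks 9-12 will be lower than weeks 1-8 even when withdrawing MapTrek changes nothing. A difference of phase means would then be read as a MapTrek effect. A concurrent control, as in the cited trial, shares the decline and cancels it; a later period in the same people does not.

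The same decline lowers the last active week relative to baseline, so it works against MapTrek in the baseline contrasts of Section 9.1. The two Fitbit-only comparators, baseline and weeks 9-12, could therefore disagree for a reason unrelated to MapTrek.

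**Working it through.** **The plan's own figure.** Section 9.2 gives 42 participants for a 1,750-step difference, SD 2,000, 80% power and alpha 0.05. The two-group formula gives 2 × (1.960 + 0.842)² × 2,000² / 1,750² = 20.5, so 21 per group and 42 in total. The figure reproduces. It is used below only as a sample size.

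**Inputs.** Active phase: days 1-56, midpoint 28.5. Fitbit-only phase: days 57-84, midpoint 70.5 (both from Section 1.1). Slope: 24.3 steps/day lost per day (Section 4.2). Assumptions: the office-worker slope applies here, MapTrek has no effect, the test is two-sided at 0.05, n = 42, and the SD of within-person change is 2,000. Section 9.2 does not say what its SD of 2,000 refers to.

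**Is 24.3 a loss per day?** The cited initial gap of 2,183 and mean gap of 1,455, closing at 44.8 − 24.3 = 20.5 per day, imply 2 × (2,183 − 1,455) / 20.5 = 71 days of observation. That is a plausible length, so the per-day reading fits. It also means that days 72-84 here lie beyond the period in which the slope was seen.

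**Bias in the 8-week mean against weeks 9-12.** With linear decline to day 84 it is 24.3 × (70.5 − 28.5) = 24.3 × 42 = 1,021 steps/day, or 58% of 1,750. This needs a total fall of 24.3 × 84 = 2,041 steps/day. Section 4.2 says that steps moved back towards baseline, so the decline may stop earlier. If it stops on day T, the bias is 24.3 times the difference between the two phases' averages of min(day, T):

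| Decline stops on day | Average in weeks 9-12 minus average in weeks 1-8 | Bias, steps/day | False-positive rate |
|---|---|---|---|
| 84 (linear throughout) | 70.5 − 28.5 = 42 | 1,021 | 90% |
| 70 | 66.75 − 28.5 = 38.25 | 929 | 84% |
| 56 | 56 − 28.5 = 27.5 | 668 | 56% |
| 42 | 42 − 26.625 = 15.375 | 374 | 22% |
| 28 | 28 − 21.25 = 6.75 | 164 | 8% |

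The false-positive rate is the power of a paired t-test with noncentrality bias / (2,000/√42). For 1,021 the noncentrality is 3.31. With an SD of change of 2,828 (2,000 in each period, uncorrelated), the top row falls to 63%.

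**Last active week (midpoint day 53) against weeks 9-12.** Linear throughout: 24.3 × 17.5 = 425 steps/day, false-positive rate 27%. If the decline stops on day 56: 24.3 × 3 = 73 steps/day, 6%. If it stops on day 42 or 28: zero bias.

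**Week 8 against week 9.** The midpoints are 7 days apart, so the bias is at most 24.3 × 7 = 170 steps/day, 8%.

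**The case against.** The strongest reply is that the largest figures belong to a comparison Section 9.1 does not list. None of its hypotheses uses an 8-week active mean or sets active weeks against weeks 9-12, and for the contrasts it does list the decline works against MapTrek. Section 3 treats week 12 as a question of maintenance. This stands, and it limits the point to the control comparison promised in Section 1.1. It does not remove the point, because that comparison is a stated purpose of weeks 9-12 and has no prespecified method.

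Second, the predicted daily decrease in Section 9.1 implies a slope within the active phase, and Section 9.4.2 names mixed models. So it would be wrong to say that the plan has no time element at all, or that an ANOVA on phase means is certain. What is missing is a statement that any such slope enters the control comparison.

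Third, carry-over of walking habits into weeks 9-12 would raise those weeks and shrink the apparent effect. That also stands: the sign of the net bias is not known.

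Finally, the single-arm pilot design is declared openly. Declaring it does not justify calling a later period a control without qualification.

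**Conclusion.** The point holds in a limited form. The control comparison in Section 1.1 is confounded with time, and the documents specify nothing that separates MapTrek's removal from ordinary decline. If it is made on phase means and the cited slope applies, the bias from decline is between 164 and 1,021 steps/day for the 8-week mean over the stopping days examined. It is at most 425 for the last active week, and 73 or less if the decline ends by day 56.

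A reader might infer that the plan will credit MapTrek with about 1,000 steps/day, or that its primary tests carry a 90% false-positive rate. The documents do not support that. Those figures are a ceiling for an unlisted contrast. They rest on a slope from office workers carried linearly to day 84, and they leave out carry-over. The change is worth making because it is cheap and the comparison cannot be interpreted without it.

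**What to change.** **Section 9.4.2.** Estimate the control comparison with a mixed model on daily steps that has a linear trend within the active phase and a level change and slope change at removal after week 8. Report the level change at removal as the MapTrek-versus-Fitbit-only estimate. Interpret it as the effect remaining at week 8, possibly attenuated by carry-over, and not as the average effect over eight weeks. On the cited figures the gap remaining at day 56 would be 2,183 − 20.5 × 56 = 1,035, against a mean of 1,455.

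**Change at MapTrek start.** Report it as a level change without a fitted pre-intervention trend, unless the two-week baseline of Section 6.1.1 applies. Section 1.1 gives four days, which cannot support a trend. The two sections must be reconciled.

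**Sensitivity analysis.** Compare week 8 with week 9, where the same decline accounts for at most about 170 steps/day.

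**Section 1.1.** State that weeks 9-12 are a non-concurrent control and that a lower mean there is not by itself evidence of a MapTrek effect.

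**Cost.** Wording and modest analysis work. Section 8.1 already provides Fitbit data for each day of wear, so no participants or measurements are added. The trend-adjusted estimate has a wider confidence interval than a difference of phase means and relies on an approximately linear trend within each phase.
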